- 5. Perform debridement if indicated. Debridement is to be performed using curette, scissors, scalpel, or forceps.
- 6. Collect 4 tissue specimens. Two in RNA later and two in DNA/RNA shield.
- 7. Perform standardized photography and measurement of the study wound (eKare or available camera with ruler). Assess the post-debridement ulcer area (cm²), perimeter (cm), and greatest depth (cm) using the inSight device (eKare, Fairfax, VA). These values are the baseline measurements for assessing accelerated wound closure at the two-week run-in visit.
- 8. Perform baseline SPP (note this procedure can be performed at any visit from baseline up to therapy initiation but before therapy is started).
- 9. Perform baseline tcpO2 (note this procedure does not need to be performed at baseline visit and can be performed at any visit through Run-In week 2/Therapy initiation visit).
- 10. Perform baseline hyperspectral imaging assessment on the dorsal and plantar aspects of the foot.
- 11. Perform neuropathy and pain assessment.
- 12. Obtain results from SOC hematology, blood chemistry, etc. that were not covered in inclusion/exclusion studies.
- 13. Subjects who do not meet eligibility and fail to qualify to enter the Run-in will be deemed Screen failures and discharged, noting the reasons for disqualification.
- 14. Collect all relevant concomitant medication (antibiotics, antifungals and other antiinfective therapies)
- 15. Wounds will be dressed SOC and offloaded per physician discretion.
- 16. Subjects who qualify to enter the run-in will be instructed to refrain from using excluded medications and return to the office for Run-in Visit 2 within 7 (±4) days.

Run-In Procedures/Therapy Initiation

Week 1 Run-in:

- 1. Assess target ulcer.
- 2. Perform debridement if indicated. Debridement is to be performed using a curette, scissors, scalpel, or forceps.
- 3. Perform standardized photography of the study wound.
- 4. Assess the post-debridement ulcer area (cm²), perimeter (cm), and greatest depth (cm) using the inSight device.
- 5. If wound size (ulcer area) increases/decreases by 30% or more, patient will be deemed a screen failure and removed from the study.
- 6. If wound size (ulcer area) decreases by less than 30%, patient wound will be treated with standard of care and return for run-in Week 2 Run-In within 7 (±4) days.

- 8. Perform pain assessment.
- 9. Collect all relevant concomitant medication (antibiotics, antifungals and other antiinfective therapies)

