7. Perform hyperspectral imaging assessment on the dorsal and plantar aspects of the foot.

10. Wounds will be dressed SOC and offloaded per physician discretion.

Week 2 Run-in/Therapy Initiation:

- 1. Assess target ulcer
- 2. Perform debridement if indicated. Debridement is to be performed using curette, scissors, scalpel, or forceps.
- 3. Perform standardized photography of the study wound.
- 4. Assess the post-debridement ulcer area (cm²), perimeter (cm), and greatest depth (cm) using the inSight device.
- 5. If wound size (ulcer area) increases/decreases by 30% or more, patient will be deemed a screen failure and removed from the study.
- 6. If wound size (ulcer area) increases/decreases by less than 30%, patient wound will enter the study and randomized to either the Celliant Active or Control treatment arm.
- 7. Perform hyperspectral imaging of the dorsal and plantar aspects of the foot
- 8. Perform pain assessment.
- 9. Collect all relevant concomitant medication
- 10. Wound will be dressed with SOC and either Celliant Active or Control Sock applied.
- 11. Wound will be offloaded.
- 12. Provide subject with any additional medical socks needed until the next visit. Instruct the subject to change the socks if they become wet, soiled, or bloody and under any conditions dictated by PI instructions.

Therapy/Treatment Phase

Study Visit 1-11:

- 1. Document study compliance information from the subject
 - a. Amount of time the sock was worn throughout the week
 - b. Was it worn during the day/night?
 - c. When/why the sock was changed.
 - d. Has the sock been on in the 3 hours leading up to the appointment?
- 2. Remove sock and dressing and immediately perform hyperspectral imaging of the dorsal and plantar aspects of the foot if wound is active or closed.
- 3. Assess target ulcer (if wound has closed, document as such, perform steps 7 and 8 and

- skip to Study Visit Wound Closed).
- 4. Debridement is to be performed, if indicated, using curette, scissors, scalpel, or forceps. If debridement is necessary at weekly visits, all therapy must be removed and replaced post-debridement.
- 5. Collect 4 tissue specimens at week 3 and at week 6. Two in RNA later and two in DNA/RNA shield.
- 6. Perform standardized photography of the study wound.
- 7. Assess the ulcer area (cm²), perimeter (cm), and greatest depth (cm) using the inSight device if the wound is deemed closed by the physician, skip to EOS visit.

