The primary population for the effectiveness analyses will be the intent-to-treat (ITT) population, which will include all randomized subjects regardless of whether the socks were ever worn. Subjects will be assessed to the group to which they were randomized, regardless of whether they were provided the wrong socks.

A secondary population for effectiveness analyses will be the (AT) population, including subjects that attempted to put on the sock for any amount of time. These subjects will be analyzed according to the type of socks (Celliant or Placebo) they received. This population is also the safety population, which is the population used for all safety analyses.

A third population is the modified full analysis set (mFAS), which consists of all subjects that report wearing the sock as directed for at least 10 days.

Sample Size Justification

Assuming a 2-sided alpha at 0.05, and a power of 0.85, the true mean difference at 12 weeks between groups in percent change in tissue oxygenation as measured by hyperspectral imaging is estimated to be 8.2 with a standard deviation of 21.7. At a 1:1 allocation of experimental to control subjects, a total of 254 evaluable subjects are required. The sample size will increase to account for attrition at Week 12.

Analyzing the sample size for the key secondary endpoint of incidence of complete wound closure suggests a much large trial is need. Specifically, at 2500 evaluable total subjects, there would be approximately a power of 0.85 to detect a difference in incidence of complete wound closure at 12 weeks if the expected incidence of complete wound closure was 25% in the experimental group, and 20% in the control group, an absolute difference of 5% between the experimental group and the control group.

Primary Efficacy Analyses

The primary efficacy endpoint is an inferential test of whether the Treatment Group (Celliant[®] Diabetic Medical Sock) percent change in tissue oxygenation (via oxygen saturation, S_tO₂) compared to the Control Group (placebo sock) at 12 weeks is superior.

Effectiveness variables will be analyzed relative to the mean of the Weekly visit 0 and -1 tissue oxygenation measurements. For purposes of statistical analysis, this mean will be referred to as the baseline.

The hypotheses are:

```
H0: %ChgPerfCelliant ≤ %ChgPerfPlacebo
Ha: %ChgPerfCelliant > %ChgPerfPlacebo
```

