A mixed model repeated measures (MMRM) will be utilized to model percent changes in tissue oxygenation by visit through 12 weeks from baseline to provide the contrast statement at 12 weeks between groups. Included in the model will be treatment group, the stratification variables of wound size (as a continuous variable) and study site. Success on this endpoint requires that the 12-week treatment group contrast difference is α <0.025. There is no interim analysis for the primary endpoint. The primary endpoint is based on a fixed study design. Regulatory activities for all but the key secondary endpoint will begin if this primary endpoint is met.

Interim Analysis for the Key Secondary Endpoint

The key secondary endpoint will only be tested for significance if the success criterion for the primary endpoint are met at the time of the primary endpoint analysis in 254 evaluable subjects, which is the interim analysis for the key secondary endpoint.

The key secondary endpoint is an inferential test of whether the Treatment Group (Celliant sock) incidence of complete wound closure rate (CWCR) compared to the Control Group (placebo sock) at 12 weeks is superior.

The hypotheses for this endpoint are:

```
H0: CWCR Celliant ≤ CWCR Placebo
Ha: CWCR Celliant > CWCR Placebo
```

The key secondary endpoint of incidence of complete wound closure at 12 weeks will be blinded except to the unblinded Interim Analysis Committee (IAC) until the final analysis for this endpoint is conducted. Since the estimated sample size for the key secondary endpoint is anticipated to be many times larger than for the primary endpoint and there is some uncertainty relative to the anticipated treatment effect, the hierarchical design allowing for the testing of the key secondary endpoint, and then the use of the adaptive group sequential design to allow for the potential of sample size re-estimation is required for efficiency.

The IAC is comprised of an unblinded statistician and a subject area medical expert whose sole responsibility is to analyze the key secondary endpoint at 254 evaluable subjects to determine, according to the Lan-Demets O-Brien Fleming alpha spending function, tested at half of the trial information:

- 1) The criterion of early stopping for efficacy for CWCR is met at half of the trial information,

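### Baseline StO2 is imaged after any debridement and on-treatment StO2 before it: the between-arm test stays valid, but each arm's percent change can carry a debridement shift, with some rescaling and possible loss of power

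*Combined protocol and SAP*

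**What the plan says.** All references are to the combined protocol and SAP.

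- **Analysis baseline** (section 4, Primary Efficacy Analyses): "Effectiveness variables will be analyzed relative to the mean of the Weekly visit 0 and -1 tissue oxygenation measurements".
- **Visit -1** (section 3, Week 1 Run-in): step 2 reads "Perform debridement if indicated. Debridement is to be performed using a curette, scissors, scalpel, or forceps". Post-debridement measurement is step 4 and hyperspectral imaging is step 7.
- **Visit 0** (Week 2 Run-in/Therapy Initiation): debridement is again step 2, and step 7 reads "Perform hyperspectral imaging of the dorsal and plantar aspects of the foot". The sock goes on at step 10.
- **Visits 1-11**: step 2 reads "Remove sock and dressing and immediately perform hyperspectral imaging of the dorsal and plantar aspects of the foot". Debridement, where needed, is step 4.
- **Week 12/EOS**: the same imaging instruction is step 4. The list has no debridement step, although the Schedule of Events marks its combined wound-assessment and debridement row for that visit.
- **Randomization and Blinding Procedure**: debridement is placed after the run-in evaluation, with randomisation at the end. This does not fit the week 0 list, where debridement comes near the start of the visit.
- **Vascular Assessment**: the imaged region is the skin around the ulcer and the dorsal and plantar angiosomes.
- **Wound Measurements and Debridement**: debridement removes the callus around the wound and continues until the bed bleeds.

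**The concern.** The primary endpoint is a percent change, so anything that alters the baseline image alters the denominator. If the steps are followed as listed, the denominator is measured on tissue that may just have been debrided, and the numerator on tissue that has not been debrided at that visit. The imaged skin adjoins the debrided tissue, so an effect on the reading is plausible, and no interval between debridement and imaging is set.

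Three things are at stake: how each arm's change from baseline can be read, the scale of the estimated difference, and precision. Precision enters because debridement is done only where the clinician finds it necessary, so some baselines would be shifted and others not. The planned mixed model contains treatment, wound size and site, and no term that would absorb this.

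**Working it through.** **1. Reproduce the plan's figure.** Inputs from Sample Size Justification: "Assuming a 2-sided alpha at 0.05, and a power of 0.85"; the difference "is estimated to be 8.2 with a standard deviation of 21.7"; equal allocation, with a stated total of 254 evaluable. The primary analysis uses one-sided 0.025 ("Success on this endpoint requires that the 12-week treatment group contrast difference is α <0.025"), which gives the same n.

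n per arm = 2 × 21.7² × (1.960 + 1.036)² / 8.2² ≈ 126, or 252 in total. With the noncentral t, power is 0.848 at 126 per arm and 0.851 at 127, so 254 is reproduced.

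**2. Uniform shift.** Let d be the acute proportional effect of debridement on StO2, an assumption because the documents give none. Baseline B is recorded as B(1+d), so:

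- control arm with no true change: 100 × [1/(1+d) − 1]
- between-arm difference: 8.2/(1+d)
- SD: 21.7/(1+d)

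| d | Control arm shows (%) | Difference (points) | SD |
|---|---|---|---|
| −20% | +25.0 | 10.25 | 27.1 |
| −10% | +11.1 | 9.11 | 24.1 |
| −5% | +5.3 | 8.63 | 22.8 |
| 0 | 0 | 8.20 | 21.7 |
| +5% | −4.8 | 7.81 | 20.7 |
| +10% | −9.1 | 7.45 | 19.7 |
| +20% | −16.7 | 6.83 | 18.1 |

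Difference and SD scale together, so power stays at 0.853 (normal approximation). At d = +10%, an active arm with a true rise of 8.2% would show 100 × (1.082/1.10 − 1) = −1.6%.

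If only one of the two baseline images follows debridement, as the narrative would imply for week 0, the mean baseline is B(1 + d/2). A 10% shift then acts like the 5% rows.

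**3. Uneven shift.** Simulation with two-sample t-tests, 127 per arm and 20,000 runs, using the same debridement process in both arms. Control is the mean change with no true effect. The last column lets d vary between subjects with SD 10 points.

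| Subjects debrided | Mean d | Control, fixed d (%) | Difference, fixed d | Power, fixed d | Power, varying d |
|---|---|---|---|---|---|
| 50% | −10% | +5.6 | 8.67 | 0.83 | 0.76 |
| 50% | +10% | −4.6 | 7.86 | 0.83 | 0.80 |
| 50% | +20% | −8.3 | 7.54 | 0.78 | 0.76 |
| 100% | −10% | +11.1 | 9.10 | 0.85 | 0.74 |
| 100% | +10% | −9.1 | 7.45 | 0.85 | 0.78 |
| 100% | +20% | −16.7 | 6.84 | 0.85 | 0.79 |

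With no true sock effect, one-sided type I error was 0.023-0.027 in every scenario, and the mean difference stayed within 0.05 points of zero.

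**4. A second set of assumptions.** With 80% of baseline visits debrided, the two baseline visits averaged, and shifts of 5-20% in either direction, the difference is 7.1-9.7 points. Power is 0.81-0.85 for a fixed shift and 0.75-0.83 with SD 10%. With SD 20% it is 0.57-0.73.

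**The case against.** The strongest reply is that nothing decisive depends on the within-arm change. The endpoint, objective, hypotheses and model contrast all compare arms, and no within-arm success criterion exists. This stands. A reader might infer that the sock effect itself is biased, or that a false effect could arise. The documents do not support that. Both baseline images precede sock application, the procedure is the same in both blinded arms, and debridement comes before randomisation on either description of week 0.

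A reader might also infer that the proposed indication rests on a within-arm increase. It does not: the sentence under Proposed Indications for Use goes on to compare with subjects wearing non-Celliant socks.

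Next, the lists are not stated to be strict sequences, and the narrative contradicts the week 0 list. This stands as a limit on certainty about what sites do. It does not remove the point: the run-in lists call for post-debridement measurement before imaging is reached, the on-treatment lists ask for immediate imaging, and the week 0 conflict itself needs resolving.

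Third, imaging targets periwound skin and angiosomes, not the wound bed, so d could be small. That is fair, although debridement also removes surrounding callus.

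Last, every power loss comes from assumed inputs. That is true, and values near 0.57 need an extreme combination.

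**Conclusion.** The point holds as a mismatch in measurement conditions, not as a threat to the validity of the primary test. As listed, the denominator of the primary endpoint is measured after any debridement and the follow-up values before it. Each arm's change from baseline can therefore carry a debridement artefact, and the estimated difference is on a scale altered by about 1/(1+d).

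For assumed shifts of 5-20%, the planned 8.2 points becomes roughly 7-10. Power is about 0.78-0.85 with a fixed shift, and about 0.74-0.83 if the shift also varies with SD 10 points. These figures assume that 21.7 excludes this noise; the plan does not say how 21.7 was obtained. They also use a week-12 t-test in place of the mixed model. If d is near zero with little variation, the loss is negligible. The change is worth making because it is nearly free and the artefact cannot be removed from an image already taken.

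**What to change.** - At visits -1 and 0, make hyperspectral imaging the first step after the dressing comes off and before any debridement, as at visits 1-12. Do the same at visit -2 for consistency, although that visit is outside the analysis baseline.
- Reconcile the Randomization and Blinding Procedure text with the week 0 list, and state that imaging precedes debridement at every visit where both occur.
- For subjects already enrolled, record whether debridement was done at visits -1 and 0, and add a sensitivity analysis of the primary endpoint that adjusts for it.

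This re-orders a measurement and leaves the decision to debride untouched. The cost is an edit to the protocol and CRF, plus some images taken in subjects who then fail the 30% run-in criterion, since imaging would come before that check. The total of 254 does not change.

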Regulatory Authorities (e.g. Food and Drug Administration	Audit clinical trial for Subject protection and data integrity
Investigator/Site Staff	Collection and assessment of data for accuracy and completeness

Alternatives to Participation

Subjects are not required to participate in this research study. As an alternative to study participation, subjects will receive wound care treatment per physician discretion.

1. Trial Objectives

The objective of this trial is to evaluate percent change from baseline in tissue oxygenation (via oxygen saturation, S_tO_2) in Celliant and Control treated groups 12 weeks post initial application, as measured by hyperspectral imaging in 254 evaluable patients total when a Celliant® Diabetic Medical Sock (n=127) is worn over the patients dressing as compared to wearing a Control Medical Sock (n=127). Enrollment may include up to 2500 total subjects to meet the Key Secondary Endpoint. The Key Secondary Endpoint is to compare the incidence of complete wound closure of Celliant and Control treated groups 12 weeks post initial application*. Other secondary outcomes include wound evaluation at 3 months post complete wound closure, accelerated wound closure as measured by changes in area, depth and volume as well as treatment compliance and assessment of pain reduction.

*if the study wound is deemed closed on the week 12 visit, the patient will continue using the sock and the wound will be evaluated on week 14 to confirm healed state.

2. Selection and Withdrawal of Subjects

Inclusion Criteria:

- Diagnosis of diabetes mellitus
- Subject is willing and able to wear a sports-style tube sock at least 22 hours a day.
- Ankle Brachial Index (ABI) ≥0.5 (bedside ABI is acceptable for screening purposes as the formal imaging ABI may not be resulted prior to surgery) or toe pressure of ≥30mmHg
- One or more diabetic foot ulcers (only one will be treated) that are located in the ankle area or below that has persisted a minimum of 30 days prior to the Screening visit
- Diabetic Foot Ulcers ≥0.5cm² and ≤16cm²
- Ulcer grade I or II, Stage A, I or II Stage B, according to University of Texas Wound Classification System
- 22 years of age or older

Exclusion Criteria:

- Subject has untreated osteomyelitis
- Ulcers within 5cm of target ulcer or connected by fistulas
- Ulcer has decreased by 30% or more at the end of the run-in period
- Subject has active untreated cellulitis
- Subject has active untreated charcot

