- 8. Perform SPP and tcPO2 measurements at Visit 4 (maybe be taken instead at visit 5 or 6 if subject has not been wearing their treatment sock leading up to the visit or misses this visit).
- 9. Collect all relevant concomitant medication
- 10. Perform pain assessment.
- 11. Redress the wound with standard of care (if wound is still active) and apply Celliant Active or Control Sock and apply offloading (if indicated).
- 12. Wound will be offloaded.
- 13. Provide subject with any additional medical socks needed until the next visit. Instruct the subject to change the socks if they become wet, soiled, or bloody and under any conditions dictated by PI instructions. Instruct the subject that they must wear the sock at all times and that including the 3 hours leading up to the next study visit.

Study Visit - Wound Closed

- 1. The study wound is defined as closed when there is complete skin re-epithelialization without drainage or dressing requirements confirmed by the evaluating physician at 2 consecutive study visits 2 weeks apart.
- 2. At this visit the subject will perform the EOS evaluation and enter the follow-up phase of the study.

Study Visit 12/EOS

- 1. If the study wound closes prior to the 12-week study mark, subjects will perform EOS visit at the time of wound closure. See Study Visit Wound Closed.
- 2. A subject whose wound does not close completely by week 12 will exited from the study after the week 12 wound evaluation.
- 3. Document study compliance information from the subject
 - a. Amount of time the sock was worn throughout the week
 - b. Was it worn during the day/night?
 - c. When/why the sock was changed.

- d. Has the sock been on in the 3 hours leading up to the appointment?
- 4. Remove sock and dressing and immediately perform hyperspectral imaging of the dorsal and plantar aspects of the foot if wound is active or closed.
- 5. Assess target ulcer (if wound has closed, document as such, perform steps 7-12 and skip to Study Visit Wound Closed).
- 6. If the subject still has a large enough wound, collect 4 tissue samples. Two in RNA later and two in DNA/RNA shield.
- 7. Perform standardized photography of the study wound.
- 8. Assess the ulcer area (cm²), perimeter (cm), and greatest depth (cm) using the inSight device.
- 9. Perform SPP if wound is active or closed.
- 10. Perform tcpO2 if wound is active or closed.
- 11. Perform pain assessment
- 12. Ask the subject if they thought they were in the active or control group

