The table below shows the schedule of planned events for each subject in this study.

Weekly Visits (±4 days)

	vocaty violo (± radyo)						
	SC	BL/-2	-1	BL/0	1-11	*EOS	FUP @3mo
Informed Consent	Х						
Inclusion/Exclusion	Х						
Randomization				Х			
Medical History, Social, Demographics, PE, Vitals		Х					
Lab Values		X					
Vascular - SPP		Х			X**	Х	
Vascular – tcpO2		Х			X**	Х	
Vascular - HSI		Х	Х	Х	Х	Х	
Monofilament, VPT		Х					
Wound Assessment, Debridement		Х	Х	Х	Х	Х	Х
Tissue Collection (4 pieces)#		Х			X##	Х	
Wound Photography and Measurements		Х	Х	Х	Х	Х	Х
Pain Assessment		Х		Х	Х	Х	
Sock Application				Х	Х		
Offloading				Х	Х		
Adverse Events			Х	Х	Х	Х	Х
Concomitant Medication		Х	Х	Х	Х	Х	
DFS-SF						Х	
Subject Stipend			Х	Х	Х	Х	Х
			·		•		

^{*}if subject is deemed closed at week 12, subject will be observed at week 14 and will enter FUP phase

Trial Monitoring

Monitoring visits will be conducted by representatives of Hologenix according to the U.S. CFR Title 21 Parts 50, 56, and 812 and ICH Guidelines for GCP (E6). By signing this protocol, the Investigator grants permission to the Hologenix contact and appropriate regulatory authorities to conduct on-site monitoring and/or auditing of all appropriate study documentation.

Clinical monitors, qualified by training and experience, will be responsible for monitoring and

^{**}Visit 4 only, 5 or 6 if visit 4 is missed

[#]Two for RNA later and two for DNA/RNA shield

^{##} Weeks 3 and 6

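### Closure must be confirmed two weeks apart, but the visit steps schedule a confirming look only for wounds first seen closed at week 12

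*Combined protocol and SAP*

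**What the plan says.** - **Definition.** Section 3, Study Visit - Wound Closed, item 1, requires full re-epithelialization with no drainage or dressing need, "confirmed by the evaluating physician at 2 consecutive study visits 2 weeks apart". Item 2 continues: "At this visit the subject will perform the EOS evaluation and enter the follow-up phase of the study".
- **Closure at Visits 1-11.** Step 3 sends a closed wound to the Wound Closed section after two further steps. Step 7 says "if the wound is deemed closed by the physician, skip to EOS visit". Study Visit 12/EOS, step 1, adds: "If the study wound closes prior to the 12-week study mark, subjects will perform EOS visit at the time of wound closure".
- **Closure at week 12.** The footnote in section 1 (Trial Objectives) says "if the study wound is deemed closed on the week 12 visit, the patient will continue using the sock", with evaluation at week 14 to confirm healing. The Schedule of Events footnote agrees: "if subject is deemed closed at week 12, subject will be observed at week 14 and will enter FUP phase".
- **Calendar.** The Schedule of Events has weekly visits, ±4 days. Apart from the week-14 exception, nothing stands between EOS and the follow-up visit at 3 months after closure, which may be by telehealth.
- **Analysis.** Section 4 tests the incidence of complete closure at 12 weeks. It does not say whether a first-seen or a confirmed closure counts.

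**The concern.** One written definition meets two visit paths. A wound first seen closed at week 12 is checked again at week 14. On the literal steps, a wound first seen closed at week 6 is not seen again for three months.

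Suppose each wound reopens ten days after it first looks closed. The week-12 wound fails confirmation. The week-6 wound keeps its closure and, if the reopening is found later, is recorded as a recurrence, which is a different endpoint. The same clinical course is classified by when it happened.

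Closure incidence is the key secondary endpoint. At 254 evaluable subjects it decides between early stopping, continuing to 508, re-estimation up to 2500 and futility. It must also be significant before VAS pain can be tested. A two-week observation that was never made cannot be reconstructed at analysis.

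**Working it through.** **1. Does the definition fit the calendar?** Consecutive visits are nominally 7 days apart. Only the extreme of both windows (7 + 4 + 4 = 15 days) or a missed visit brings two consecutive visits two weeks apart.

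**2. Who has a scheduled confirming look?**

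| First seen closed | Look needed two weeks later | What the literal steps provide |
|---|---|---|
| Weeks 1-10 | Weeks 3-12 (slots exist in the calendar) | EOS at closure, then 3 months |
| Week 11 | Week 13 | EOS at closure, then 3 months; no week-13 visit exists |
| Week 12 | Week 14 | Week 14 |

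**3. The plan's own figure.** Inputs from section 4, Sample Size Justification: p1 = 0.25, p2 = 0.20, 2500 evaluable subjects at 1:1 (n = 1250 per arm), power about 0.85. Alpha is 0.05 two-sided. For a fixed design with pooled variance and no continuity correction:

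power = Φ{ [ |p1 − p2|·√n − 1.96·√(2·p̄·(1 − p̄)) ] / √(p1(1 − p1) + p2(1 − p2)) }

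With p̄ = 0.225: (0.05 × 35.355 − 1.96 × 0.5906) / 0.5895 = (1.7678 − 1.1575) / 0.5895 = 1.035, and Φ(1.035) = 0.850. Solving for n gives 1251 per arm, 2502 in total. The stated figure reproduces.

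**4. What confirming every closure could cost.** The documents do not give the share f of first-look closures that fail a two-week check. I assume f of 5-20%, equal in both arms, and treat 25% and 20% as first-look rates. Each rate becomes p(1 − f).

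| f | Rates | Power at 2500 | Total N for 0.85 |
|---|---|---|---|
| 0 | 25.0% v 20.0% | 0.850 | 2502 |
| 5% | 23.75% v 19.0% | 0.826 | 2672 |
| 10% | 22.5% v 18.0% | 0.800 | 2862 |
| 20% | 20.0% v 16.0% | 0.740 | 3310 |

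If 25% and 20% are already confirmed rates, the first row applies whatever f is.

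**5. The literal routing instead.** Suppose 80% of closures come before week 12 (assumed), count on one look, and only week-12 closures can fail. The rates are p[0.8 + 0.2(1 − f)]. At f = 5% this is 24.75% v 19.8%, power 0.845. At f = 20% it is 24.0% v 19.2%, power 0.831. The two readings give different closure rates from the same patients.

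**6. Interim sensitivity (illustration).** With 127 per arm, 25% v 20% is about 32 v 25 closures, z = 1.05. Reclassifying three closures in the Celliant arm alone gives 29 v 25, z = 0.61. This is one-sided by construction. It shows only that a handful of classifications matters at that look.

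**The case against.** The strongest reply is that there is only one written definition and early closers are sent to the very section that contains it. The EOS instruction there could mean the confirming visit, so that the time of wound closure means closure as defined. The Visit 1-11 steps also provide for imaging a closed wound, and for applying the sock when the wound is no longer active. For wounds first seen closed by week 10, a visit two weeks later already exists. On this view, week 12 needed a footnote only because week 14 lies outside the calendar.

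That reading is possible, so a reader who infers two written standards goes too far: the split comes from the literal visit steps. Three things count against the benign reading. Section 1 uses *deemed closed* for a first sighting still awaiting confirmation, and Visit 1-11 step 7 uses the same words to trigger EOS. No week-13 look exists for week-11 closers. The 28-week maximum equals 1 + 2 + 12 + about 13 weeks, which fits follow-up counted from a week-12 first sighting; counting from confirmation at week 14 would give about 30. Even if the benign reading was intended, two sites could apply the steps differently.

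A reader might also infer bias in favour of the sock. The documents do not support that. Both arms follow the same blinded flow, and with equal closure timing and equal failure shares the shift is zero. As an illustration (all assumed), take equal first-look closure of 20% per arm, 85-90% v 80% of closures before week 12, and f of 5-20%. The shift is 0.20 × f × the difference in early share: from 0.20 × 0.05 × 0.05 = 0.05 to 0.20 × 0.20 × 0.10 = 0.4 percentage points. It would favour whichever arm closes earlier, and it requires a real timing difference.

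**Conclusion.** The point holds as a contradiction in the key secondary endpoint. The definition does not fit the weekly calendar. Followed literally, the steps leave wounds closing before week 12 either unable to meet the definition or counted on a single look, while week-12 closers are re-examined. Section 4 does not resolve which status is analysed.

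The direction and size of any between-arm bias cannot be determined from the documents. It would be tempting to read the power range of 0.83-0.74 as the harm done by the mixed rule. It is not: it is the cost of confirming every closure, on the assumptions that 25% and 20% are first-look rates and that 5-20% fail equally in both arms. If the planned rates are already confirmed rates, the cost is nil. The case for correction rests on an endpoint that cannot be classified consistently, not on those figures.

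**What to change.** Reconcile the section 1 footnote, the Visit 1-11 steps, the Wound Closed and Visit 12/EOS sections and the Schedule of Events, so that the protocol's own two-week confirmation applies to every closer:

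1. Redefine confirmation as two assessments at least two weeks apart with no open assessment between them. Give the confirming visit its own window, because ±4 days at each end lets visits nominally 14 days apart fall 6 to 22 days apart.
2. In the Visit 1-11 steps, make the confirming visit, not the first sighting, the trigger for EOS and follow-up.
3. Schedule the look at week 13 or 14 for closures first seen at week 11 or 12.
4. In section 4, state that confirmed closure is analysed, which date counts for the 12-week endpoint, and how an unconfirmed closure or a missed confirmation visit is classified.
5. State whether 25% v 20% are confirmed rates; if not, revisit the power statement.

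Sock use between first sighting and confirmation is described explicitly only for week-12 closers. Those passages also need reconciling; I propose no rule.

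The cost is protocol and SAP wording, one new visit slot for week-11 closers, and possibly a slightly lower closure rate. Early closers would stay in the study up to two weeks longer, mostly on weekly slots that already exist. The change should be made before closures are classified for the interim.
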